The efficacy and safety of DCA in reducing the SMF have been demonstrated in multiple phase I to III clinical studies. (5). Phase I studies demonstrated that DCA administration did not significantly impact on liver function, kidney function, heart rate, or levels of cholesterol, triglycerides, free fatty acids, or proinflammatory cytokines (6,7). Phase II studies examined treatment regimens and dosages, revealing that the optimal dose for DCA was 2mg/cm² administered via 0.2 ml injections spaced 1 cm apart in the submental area. The recommended injection interval was 28 days (8, 9). Phase III studies have shown the efficacy and safety of DCA in SMF reduction. Accordingly, in a 12-week double-blind, placebo-controlled study including physician examinations, patient satisfaction, and MRI fat mass measurements, the clinical evaluation revealed that 70% of the individuals who received the medicine showed one grade of improvement in SMF score. Additionally, 13.4% of the subjects demonstrated two grades improvement, while no improvement was observed in the placebo group. These findings underscore the safety and effectiveness of the drug in treating moderate to severe submental fat. In the MRI evaluation, the proportion of responders was significantly higher in the intervention group compared to placebo group (46.3% vs. 5.3%; p < 0.001). Researchers concluded that DCA is an effective and safe injectable drug in reducing SMF (10).

The drug is administered to individuals aged 18 to 65. Common adverse events included pain, swelling, hematoma, and bruising at the injection site. There were some rare case reports, of damage to the mandibular nerve resulting in an asymmetric smile that generally resolves without any intervention (11). Another potential side effect is dysphagia, and the drug is contraindicated for individuals with a history of dysphagia (12).

The purpose of this study is the safety and efficacy assessment of Embella® injectable solution containing deoxycholic acid (manufactured by Espad Darou Pharmed Company) for the reduction of unwanted submental fat.

Objectives

Primary objective:

- Safety and efficacy assessment of Embella® injectable solution in reducing the unwanted submental fat.

Secondary objectives:

- Assessment of the efficacy of Embella® injectable solution, in improving the standard grading of submental fat (SMF)
- Assessment of the efficacy of Embella® injectable solution in reducing the diameter of submental fat

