- The product is a 2 ml sterile, transparent, and colorless vial containing 20 mg of DCA. Additional ingredients include hyaluronic acid, water for injection, sodium chloride, sodium hydroxide, hydrochloric acid, and disodium phosphate anhydrous.
- Use of ice/cold packs, topical and/or injectable local anesthesia (e.g., lidocaine) may enhance patient comfort.

Method of administration

The product is indicated for subcutaneous administration only.

[figure not shown]
EMBELLA® is supplied in ready-to-use, single-use vials. Gently invert the vial several times before use. Do not dilute.

EMBELLA® shall be prepared for injections in the following way:

1. Remove the flip-off cap from the vial and clean the penetrable stopper of the vial with an antiseptic. If the vial, seal, or flip-off cap is damaged, do not use it.
2. Attach a large bore sterile needle to a sterile single-use 1 ml syringe.
3. Introduce the large bore sterile needle into the stopper of the vial and draw 1ml of EMBELLA® into the 1ml syringe.
4. Replace the large bore needle with a 30 gauge (or smaller)-0.5-inch needle. Expel any air bubbles in the syringe barrel before injecting the product into the subcutaneous fat.
5. To withdraw the remaining contents of the vial, repeat steps 3 and 4.

[figure not shown]
For injection, the needle is inserted perpendicular to the skin, and injection should be avoided in the area defined by a line 1 to 1.5 cm from the angle of the mandible to the mentum (Figure 1).

Figure 1. Avoid the Marginal Mandibular Nerve Area

[figure not shown]
Avoid injection into the platysma. Prior to each treatment session, palpate the submental area to ensure sufficient submental fat and to identify subcutaneous fat between the dermis and platysma (pre-platysmal fat) within the target treatment area (Figure 2).

Figure 2. Sagittal View of Platysma Area

Outline the planned treatment area with a surgical pen and apply a 1 cm^2 injection grid to mark the injection sites (Figures 3).

Figure 3. Injection Pattern

WARNINGS AND PRECAUTIONS

- Embella[®] should only be injected within the defined parameters. Each vial is intended for use in one patient and should be discarded after use.
- Store the product between 15°C and 30°C.
- Use of ice/cold packs, topical and/or injectable local anesthesia, and NSAIDs may enhance patient comfort.

[figure not shown]
[figure not shown]
[figure not shown]
[figure not shown]
[figure not shown]
[figure not shown]
[figure not shown]
Endpoints

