Primary and secondary endpoints are evaluated before injection and 4 and 12 weeks after the last injection.

Primary Endpoint

At least one-grade improvement in standard grading of submental fat (SMF) evaluated at 4 and 12 weeks after the last injection (Figure 4)

Figure 4: Standard grading of submental fat (SMF)

| Scale | 0 | 1 | 2 | 3 | 4 |
|----------------------------|---|---|--|---|---|
| Submental Convexity | Absent | Mild | Moderate | Severe | Extreme |
| Description | No localized submental fat evident | Minimal localized submental fat | Prominent localized submental fat | Marked localized submental fat | Extreme submental convexity |
| Representative Photographs |  |  |  |  |  |
| |  |  |  |  |  |
| |  |  |  |  |  |

Secondary Endpoints

- Submental fat diameter will be measured with the calliper at 4 and 12 weeks after the last injection
- Intensity of procedural pain will be assessed using the Visual Analogue Scale (VAS), ranges from 0 (complete painlessness) to 10 (maximum pain).
- Patient satisfaction will be assessed using the Visual Analogue Scale (VAS), ranges from 0 (not satisfied at all) to 10 (maximum satisfaction).
- Any observed or reported adverse events will be recorded after the injections and at 4 and 12 weeks follow-up visits, graded as mild [1] moderate [2] and severe [3].

Study Timeline

| Visit No | 0 | 1 | 2 | 3 | 4 | 5 | 6 |
|--|----------|-------------|---|---|------------------------|---|---|
| | Day 1 | | | | | | |
| Time | Baseline | Injection 1 | Week 4 (± 2 days) (Injection 2)/ Follow-up of subjects with a satisfactory response who do not require further treatment | Week 8 (± 4 days) (Injection 3)/ Follow-up of subjects with a satisfactory response who do not require further treatment | Week 12 ± 4 day | Week 16 ± 4 day (In subjects with 2 injections) | Week 20 ± 4 day (In subjects with 3 injections) |
| Screening | X | | | | | | |
| eligibility control | X | | | | | | |
| Consent | X | | | | | | |
| Demographic data | X | | | | | | |
| Injection | | X | X | X | | | |
| Pain assessment | | X | X | X | | | |
| Digital Photography | X | | X | X | X | X | X |
| Measurement of submental fat | X | | X | X | X | X | X |
| Patients' satisfaction | | | X | X | X | X | X |
| Physicians' assessment According to SMF | X | | X | X | X | X | X |
| Adverse Events | X | X | X | X | X | X | X |

Study Visits:

Visit 0: Screening & eligibility control

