The following screening procedures will be conducted to determine eligibility: The investigator will evaluate each patient against the inclusion and exclusion criteria. If the patient is eligible to participate in the study, the study process will be explained to them in an understandable and verbal manner, and a consent form will be provided. Once the information presented to the patient has been thoroughly reviewed and understood by them, and they have received the necessary explanations, the patient will be asked to write their full name on the consent form and sign it. Following the completion of these steps, the following actions will be carried out:

- Digital AP and lateral photography of the patient's neck
- Grading of submental fat based on SMF
- Measurement of submental fat diameter

Visit 1 (day 1):

- Solution injection by the physician
- Monitor the patient for up to half an hour after injection
- Reporting and recording adverse events
- Pain assessment

Visit 2 (4 weeks±2 days):

In case of complete recovery with the physician's opinion:

- Digital AP and lateral photography of the patient's neck
- Grading of submental fat based on SMF
- Measurement of submental fat diameter
- Reporting and recording adverse events
- Evaluation the patient satisfaction

If re-injection is needed:

- Solution injection by the physician
- Monitor the patient for up to half an hour after injection
- Digital AP and lateral photography of the patient's neck
- Pain assessment
- Reporting and recording adverse events

Visit 3 (8 weeks±4 days):

In case of complete recovery with the physician's opinion:

- Digital AP and lateral photography of the patient's neck
- Grading of submental fat based on SMF
- Measurement of submental fat diameter
- Reporting and recording adverse events
- Evaluation the patient satisfaction

If re-injection is needed:

- Solution injection by the physician
- Monitor the patient for up to half an hour after injection
- Digital AP and lateral photography of the patient's neck
- Pain assessment
- Reporting and recording adverse events

Visit 4 (12 weeks±4 days):

- Digital AP and lateral photography of the patient's neck
- Grading of submental fat based on SMF
- Measurement of submental fat diameter
- Reporting and recording adverse events
- Evaluation the patient satisfaction

Visit 5 (16 weeks±4 days) (In subjectswith 2 injections):

- Digital AP and lateral photography of the patient's neck
- Grading of submental fat based on SMF

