- The patients were allowed and free to refuse to cooperate with the study and follow-up whenever they want, but the researchers try to collect the maximum information, including the reasons for leaving the study and, if possible, the final results of the treatment.
- If a patient missed 2 or more consecutively scheduled visits, he/she was dismissed from the study.
- Occurrence of any of the exclusion criteria
- Occurrence of serious adverse event (SAE).

Randomization

Since this is a single-group study, randomization is not applicable.

Sample size

This study will be conducted in 20 eligible participants.

Section 4: Outcome Variables

Endpoints

Primary and secondary endpoints are evaluated before injection and 4 and 12 weeks after the last injection.

Primary Endpoint

At least one-grade improvement in standard grading of submental fat (SMF) evaluated at 4 and 12 weeks after the last injection (Figure1).

Figure 1: Standard grading of submental fat (SMF)

Scale	0	1	2	3	4
Submental Convexity	Absent	Mild	Moderate	Severe	Extreme
Description	No localized submental fat evident	Minimal localized submental fat	Prominent localized submental fat	Marked localized submental fat	Extreme submental convexity
Representative Photographs					

Secondary Endpoints

- Submental fat diameter will be measured with the calliper at 4 and 12 weeks after the last injection
- Intensity of procedural pain will be assessed using the Visual Analogue Scale (VAS), ranges from 0 (complete painlessness) to 10 (maximum pain).
- Patient satisfaction will be assessed using the Visual Analogue Scale (VAS), ranges from 0 (not satisfied at all) to 10 (maximum satisfaction).
- Any observed or reported adverse events will be recorded after the injections and at 4- and 12-weeks follow-up visits, graded as mild [1] moderate [2] and severe [3].

Safety End point

Assessment of Adverse Events.

Adverse Event (AE) is described as any medical event that occurs in patients participating in a study, which differs from the clinical manifestations of the underlying disease progression and does not necessarily have a causal relationship with the treatment used in the study. Clinical manifestations that will be reported as adverse events include any symptoms, signs (such as any abnormal laboratory results), or temporary illness related to the use of the product being studied, whether or not these effects are causally related to the product under study.

Very common adverse events of DCA include:

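### No systematic adverse event collection is set out between the stay after each injection and the next visit about 4 weeks later, so transient reactions are likely to be under-reported

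*Protocol*

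**What the plan says.** The primary objective in the Protocol (Objectives) is "Safety and efficacy assessment of Embella® injectable solution in reducing the unwanted submental fat", and SAP Section 2 repeats it. Adverse events themselves are listed as a secondary endpoint. The Protocol states: "Any observed or reported adverse events will be recorded after the injections and at 4 and 12 weeks follow-up visits". SAP Section 4 has the same sentence: "Any observed or reported adverse events will be recorded after the injections and at 4- and 12-weeks follow-up visits".

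Under Study Visits, each injection carries the instruction "Monitor the patient for up to half an hour after injection". This is a ceiling with no minimum. The timeline tables in both documents tick adverse events at Visits 0 to 6 and show no contact between an injection and the next visit. Neither document mentions a diary, a telephone call, an early visit, or an instruction to report events between visits.

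The Protocol (Adverse Events) and SAP Section 4 (Safety End point) class pain, edema, numbness or tingling, swelling, bruising, erythema and itching as very common. Both class nerve injury around the jaw and dysphagia as common. The Protocol Introduction differs on nerve injury: it speaks of rare case reports of "damage to the mandibular nerve resulting in an asymmetric smile that generally resolves without any intervention".

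On comfort at the injection visit, the Protocol says: "Use of ice/cold packs, topical and/or injectable local anesthesia (e.g., lidocaine) may enhance patient comfort".

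**The concern.** The expected reactions are mostly local and many could be short-lived. They may start, peak and resolve at home, while the planned looks fall at the very start and about four weeks later. What happens in between is not collected at source.

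The plan's own classifications need that information. Severity (Protocol, Recording and Reporting of Adverse Events; SAP Section 5, Safety Analysis) turns on whether daily activities are affected, which can hardly be judged during a clinic stay of half an hour or less. The certain, probable and possible causality categories in the Protocol depend on timing relative to administration, so onset dates matter.

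Local anesthesia may still be active at the early check, so numbness or suspected nerve injury seen then is hard to interpret. The visit procedures and timeline do not list a record of whether an anesthetic was used.

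At stake is the adverse event profile of a 20-subject, single-arm study. With no concurrent group observed on the same schedule, nothing shows how much was missed.

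**Working it through.** The documents give no figure on this point to reproduce: N = 20 comes with no adverse event rate or precision target. The check is therefore arithmetic on the schedule, followed by labelled illustrations.

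**Inputs (Protocol, Study Timeline and Study Visits).** Injection 1 at day 0; Visit 2 at day 28 ± 2 (26 to 30); Visit 3 at day 56 ± 4 (52 to 60); Visit 4 at day 84 ± 4 (80 to 88). Stay of at most 0.5 h. Up to 3 injections in 20 subjects, so up to 20 × 3 = 60 sessions.

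**Gap from injection to next adverse event recording.** Shortest = earliest next visit minus latest injection visit; longest = latest next visit minus earliest injection visit.

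- Injection 1 to Visit 2: 26 − 0 = 26 to 30 − 0 = 30 days
- Injection 2 to Visit 3: 52 − 30 = 22 to 60 − 26 = 34 days
- Injection 3 to Visit 4: 80 − 60 = 20 to 88 − 52 = 36 days

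These take the windows at face value. The Intervention section asks for at least 4 weeks between sessions, which does not agree with the lower ends of the first two ranges when the next visit is also an injection. Those passages should be reconciled; the point here does not depend on it.

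**Share of time directly observed.** 0.5 / (28 × 24) = 0.5 / 672 = 0.07%. Over the windows: 0.5 / (36 × 24) = 0.06% to 0.5 / (20 × 24) = 0.10%. This is a share of time, not a capture rate.

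**Illustration 1: persistence to the next visit.** Assumption: reactions start soon after injection and have exponential durations with median m days. Share still present at day t = 2^(−t/m).

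| Assumed median m | t = 20 days | t = 28 days | t = 36 days |
|---|---|---|---|
| 3 days | 1.0% | 0.2% | 0.02% |
| 7 days | 14% | 6% | 3% |
| 14 days | 37% | 25% | 17% |

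The remainder would depend on direct observation during the stay, spontaneous report or recall.

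**Illustration 2: effect on what 20 subjects can show.** Assumptions: true per-subject risk p and share c of cases captured. Expected recorded cases = 20pc; chance of at least one = 1 − (1 − pc)^20.

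- p = 10%, c = 1: 1 − 0.90^20 = 88%
- p = 10%, c = 0.5: 1 − 0.95^20 = 64%
- p = 10%, c = 0.25: 1 − 0.975^20 = 40%
- p = 30%: expected recorded cases 20 × 0.30 = 6 with full capture, 3 with half, 1.5 with a quarter

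Neither document supplies m, p or c.

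**The case against.** The strongest reply is that the schedule is less blind than it looks. Reactions that start during the stay, or are still present at the next visit, can be seen directly. Pain is scored separately at every injection. The endpoint wording admits reported as well as observed events and does not confine reporting to the half hour, and all adverse events must go into the medical file and the CRF. The CRF is not supplied and the consent pages were removed, so a checklist, or an instruction to report between visits, cannot be excluded. Adverse events are formally a secondary endpoint, and no safety hypothesis is tested.

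All of that stands, and it limits the point. A reader might infer that short-lived reactions are never observed, or that they reach the data only through unprompted recall. The documents do not support either: they leave room for spontaneous reports, and they do not show whether questioning is prompted. A reader might also infer that the bias runs one way on every measure. Under-reporting is the plausible direction for incidence, but recalled severity and duration could err either way. Nor does the 0.07% mean that 99.93% of events are lost.

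What the reply does not supply is a planned means of collecting events between visits. Room for a spontaneous report is not a route for one.

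**Conclusion.** The concern holds in this form: the protocol and SAP set out no systematic adverse event collection between a stay of at most half an hour and the next visit, nominally 28 days later and 20 to 36 days across the windows. Reactions confined to that interval depend on spontaneous report or recall. The likely effect is understated incidence of transient reactions, and unreliable onset dates, durations and severity grades.

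The timing is certain from the documents. The number of events missed cannot be calculated, because no reaction durations are given; the persistence and capture figures are illustrations under assumed values. The primary endpoint, SMF grade improvement, is unaffected. The change should be made because safety is in the primary objective and the remedy is cheap.

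The two descriptions of nerve injury frequency, rare case reports in the Introduction and common under Adverse Events, also need reconciling.

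**What to change.** - Give each subject a one-page diary at every injection visit, covering the days to the next visit. List the reactions named in the Protocol under Adverse Events, plus asymmetric smile from the Introduction, each with start date, stop date and effect on daily activities.
- At the next visit the investigator reviews the diary with the subject and assigns the 1-3 severity grade and the causality category under the Protocol's existing definitions. The subject does not self-grade, so classification stays with the investigator.
- Add the diary to the adverse event row of both timelines after Visits 1, 2 and 3.
- Record on the CRF whether a local anesthetic was used at each session, so that early numbness can be interpreted.

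The cost is a printed page, a CRF entry and some extra data entry, with no added visit or procedure. Two downsides should be accepted openly: reported adverse event rates will probably rise, and a new patient-completed form will probably need ethics approval.

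The documents mix past and future tense. If injections are already complete, the report should state that events between visits were not systematically collected and that adverse event rates may be understated.

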- Measurement of submental fat diameter
- Reporting and recording adverse events
- Evaluation the patient satisfaction

Visit 6 (20 weeks±4 days) (In subjectswith 3 injections):

- Digital AP and lateral photography of the patient's neck
- Grading of submental fat based on SMF
- Measurement of submental fat diameter
- Reporting and recording adverse events
- Evaluation the patient satisfaction

Participants:

This study will be conducted in 20 eligible participants.

Early Termination Policy: The decision to terminate the study early, due to safety concerns or to protect patient health, will be made by the Principal Investigator (PI) or the sponsor, with mutual agreement from both parties.

Withdrawal of Subjects

- The patients were allowed and free to refuse to cooperate with the study and follow-up whenever they want, but the researchers try to collect the maximum information, including the reasons for leaving the study and, if possible, the final results of the treatment.
- If a patient missed 2 or more consecutively scheduled visits, he/she was dismissed from the study.
- Occurrence of any of the exclusion criteria
- Occurrence of serious adverse event (SAE).

Data Collection

All required data will be recorded on the (paper) CRFs for this study, which will be designed and provided by PI. The reason for any missing data will be explained. All entries must be in permanent, blue ink. Errors will have single lines drawn through them with the correct data, recorder's initials, and date entered above the error. All errors must remain legible. Erasure or obliteration of errors in the CRF or other permanent study records are strictly prohibited.

Statistical analysis:

For statistical analysis, we performed descriptive statistics (mean, standard deviation or median and range, frequency and percentages). The efficacy of the treatment was assessed by comparing the mean/median value of each parameter among visits, using the Paired Sample T-test or the nonparametric equivalent, Wilcoxon test. SPSS 24 statistical software was used for data analysis. The statistical significance level was defined as $p<0.05$.

Adverse Events

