STATISTICAL

ANALYSIS PLAN

Safety and efficacy assessment of deoxycholic acid (Embella[®]) injectable solution for the reduction of unwanted submental fat

NCT Number: NCT06509438

Date: November 20, 2022

STATISTICAL ANALYSIS PLAN

Name of Test Drug:	Embella®
Methodology:	Interventional, single-armed
Sponsor:	Espad Pharmed Darou Company
	Office:
	Espad Pharmed, [name]
	[contact]
Sponsor Representatives:	Zist Orchid Pharmed Co.
Statistical Analysis Plan Date:	November 20, 2022
Statistical Analysis Plan Version:	Version 1.0

Contents

Participate timeline	4
Section 1: Administrative information	5
Title and Trial registration.....	5
Trial registration number	5
SAP Version (SAP version number with dates)	5
Section 2: Introduction	5
Objectives.....	5
Primary objective(s):	5
Secondary objective(s):	5
Section 3: Trial Methods	5
Trial design – description of trial design	5
Inclusion Criteria	6
Exclusion Criteria	6
Withdrawal of Subjects	6
Randomization.....	7
Sample size	7
Section 4: Outcome Variables	7
Endpoints.....	7
Primary Endpoint.....	7
Secondary Endpoints	8
Safety End point	8
Section 5: Statistical analysis	10
Patient Characteristics and Baseline Comparisons.....	10
Primary and Secondary Endpoint Analysis	10
Safety Analysis.....	10
List and describe each primary and secondary outcome including details of: methods used for assumptions to	

be checked for statistical methods.....	11
Missing Data.....	11
Covariate Adjustment.....	11
Statistical Software.....	11

Participate timeline

Visit No	0	1	2	3	4	5	6
	Day 1						
Time	Baseline	Injection 1	Week 4 (± 2 days) (Injection 2)/ Follow-up of subjects with a satisfactory response who do not require further treatment	Week 8 (± 4 days) (Injection 3)/ Follow-up of subjects with a satisfactory response who do not require further treatment	Week 12 ± 4 day	Week 16 ± 4 day (In subjects with 2 injections)	Week 20 ± 4 day (In subjects with 3 injections)
Screening	X						
eligibility control	X						
Consent	X						
Demographic data	X						
Injection		X	X	X			
Pain assessment		X	X	X			
Digital Photography	X		X	X	X	X	X
Measurement of submental fat	X		X	X	X	X	X
Patients' satisfaction			X	X	X	X	X
Physicians' assessment According to SMF	X		X	X	X	X	X
Adverse Events	X	X	X	X	X	X	X

Section 1: Administrative information

Title and Trial registration

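### Does the unnamed visit comparison, with grades not listed for re-injected subjects at Visits 2 and 3, leave the efficacy tests undefined or short of data?

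*Protocol*

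**What the plan says.** **Test.** The protocol's Statistical analysis section, and the SAP's Primary and Secondary Endpoint Analysis in the same words, assess efficacy by "comparing the mean/median value of each parameter among visits", with a paired t-test or Wilcoxon test. Neither names a visit pair or a reference visit.

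**Endpoint times.** The Endpoints sections of both documents place primary and secondary evaluations before treatment and at four and twelve weeks, counted from the final injection.

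**Visit text.** For Visits 2 and 3 the protocol gives two lists. Under "In case of complete recovery with the physician's opinion" come photography, SMF grade, diameter, adverse events and satisfaction. Under "If re-injection is needed" come injection, monitoring, photography, pain and adverse events.

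**Timeline.** The tables in both documents mark the measures at Visits 2 and 3 without a footnote: "Measurement of submental fat | X | | X | X | X | X | X" in the protocol, and likewise the SAP row "Physicians' assessment According to SMF". Those two columns serve both the injection visit and "Follow-up of subjects with a satisfactory response who do not require further treatment".

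**Intervention section.** Every subject is evaluated four weeks after the first and second injections, before the decision on further treatment. The measures are not named.

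**The concern.** Visits are numbered by calendar week, while the endpoints run from the last injection, and a subject may have one, two or three injections. If the test sentence is read as comparing numbered visits, no post-baseline visit matches an endpoint time for everyone. Week 12 would then pool subjects at 12, 8 and 4 weeks from their last injection.

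The visit text adds a selection problem to that reading. If re-injected subjects are not graded at Weeks 4 and 8, a test at those visits describes only subjects the physician judged to need no more treatment, which favours the product. A three-injection subject would also have no scheduled post-baseline grade before Week 12, and the SAP imputes nothing.

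One rule for every parameter cannot mean change from baseline either. Satisfaction is first recorded at Visit 2 and pain only at injection visits. What seemed to be at stake was therefore which values are tested, and on whom.

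**Working it through.** The plan gives no figure to reproduce here; 20 subjects is stated without a power calculation. The check is schedule arithmetic.

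**Inputs.** One to three injections (Intervention); injections at Weeks 0, 4 and 8, and visits at Weeks 4, 8, 12, 16 and 20 (Study Timeline); N = 20. Assumed: exact four-week spacing, no dropout, one-injection subjects attend Visit 3 as its column header indicates, and Visits 5 and 6 are limited to two- and three-injection subjects as headed.

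**Step 1: endpoint weeks.** Last injection week = 4 × (k − 1) for k injections; add 4 and 12.

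| Injections | Last injection | +4 weeks | +12 weeks | Visits needed |
|---|---|---|---|---|
| 1 | Week 0 | Week 4 | Week 12 | 0, 2, 4 |
| 2 | Week 4 | Week 8 | Week 16 | 0, 3, 5 |
| 3 | Week 8 | Week 12 | Week 20 | 0, 4, 6 |

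**Step 2: visits with a grade and diameter under each reading.**

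| Injections | Timeline marks apply to all | Visit text followed |
|---|---|---|
| 1 | 0, 2, 3, 4 | 0, 2, 3, 4 |
| 2 | 0, 2, 3, 4, 5 | 0, 3, 4, 5 |
| 3 | 0, 2, 3, 4, 6 | 0, 4, 6 |

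In every row the visits needed in Step 1 are contained in both sets. Scheduled coverage is therefore 20/20 at +4 weeks and 20/20 at +12 weeks under either reading, whatever the split by number of injections.

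**Step 3: what differs between the readings.** The Visit 2 and 3 grades not listed in the visit text number 0, 1 and 2 per subject with one, two and three injections. Over 20 subjects the total is n2 + 2 × n3, where n2 and n3 are the numbers with two and three injections. It runs from 0 of 40 (all have one) to 40 of 40 (all have three). Each such grade is taken at a visit where the subject is injected again, so it is at neither endpoint time.

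**Step 4: the numbered-visit reading.** Six graded visits give 6 × 5 / 2 = 15 pairs, 5 of them against baseline. The pair of Visits 5 and 6 contains nobody. Pairs that every injection group can supply come from the visits common to all rows: {0, 2, 3, 4} under the timeline gives 4 × 3 / 2 = 6, and {0, 4} under the visit text gives 1. The endpoint definition needs only 2 comparisons with baseline, each aligned to the last injection.

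**Step 5: early withdrawal.** A three-injection subject who leaves before Week 12 lacks both the +4 and the +12 value under either reading. A Week 4 or Week 8 grade does not replace them, because nothing is imputed.

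**The case for a change.** The strongest case for a change is that a SAP exists to settle which values are compared, and this one uses a word that points to numbered visits. The timeline also cannot be assumed to agree with the visit text. Its marks for pain, "Pain assessment | | X | X | X", must be conditional at Visits 2 and 3, but photography, "Digital Photography | X | | X | X | X | X | X", is marked there in the same way as grade and diameter and appears in both visit lists. A CRF designer could follow either source, and a sentence plus a footnote would cost little.

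The description of the text stands. The documents do not link the test to the endpoint times, and they do not say whether the marks cover re-injected subjects. The Intervention section's general evaluation does not settle it.

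The consequence does not stand. The numbered-visit reading conflicts with the endpoint times stated in both documents, and the SAP's test sentence belongs to the endpoint analysis. A column serving two groups can list the procedures of both, with the visit text allocating them; photography would be marked under that reading too. Adding grades before re-injection supplies no value to either endpoint comparison. Spelling out the pairs would not reduce the number of tests: two at 0.05 give at most 1 − 0.95² = 0.0975 under independence, with or without the extra wording.

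**Conclusion.** No change is needed. The missing visit pair is a gap an analyst fills from the Endpoints section: baseline against four weeks, and baseline against twelve weeks, from each subject's last injection. Satisfaction is naturally summarised at those same times and pain by injection session, since neither has a baseline value. The difference between timeline and visit text affects only interim values that neither comparison uses. Scheduled endpoint coverage is 20 of 20 at both times under both readings.

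This rests on four-week spacing and no dropout. The Intervention section sets four weeks as a minimum, so a longer gap would move the calendar weeks, but the endpoint times still run from the last injection. It also rests on nobody testing Week 4 or Week 8 as numbered visits when only subjects not re-injected were measured there; such a test would fall outside the stated endpoints.

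The visit text speaks of complete recovery where the timeline speaks of a satisfactory response. These should be read together by the sponsor and investigator. The Intervention section sends everyone not re-injected to follow-up, so no visit is lost through the mismatch.
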